## **5.6.2 Analysis of Key Study Outcomes**

### **5.6.2.1 Primary Outcomes**

#### **Pattern of Chemotherapy**

The type of chemotherapy combined with Vectibix®, including start and stop dates, dose, route, frequency and reason for cessation of chemotherapy will be summarized.

#### **Summary of Vectibix® Exposure**

Starting dose and dose administered after initiation of Vectibix® will be summarized.

Cumulative dose, maximum dose, duration of exposure and number of infusions received will be summarized for the entire follow-up observation period from initiation of Vectibix®. For each subject, cumulative dose will be calculated by summing the doses of all Vectibix® infusions received across the entire observation period (ie, from initiation of Vectibix® to last dose of Vectibix®). The total number of infusions received will be calculated by summing the number of Vectibix® infusions received across the entire observation period. Similarly, duration of exposure will be calculated as the number of months between the date of the first and last Vectibix® infusions administered during the observation period (Note: a subject is considered exposed to Vectibix® if he/she received at least one infusion, irrespective of the duration of subsequent exposure). The maximum dose will be calculated as the highest Vectibix® dose administered across the

---

entire observation period. The number and percentage of subjects experiencing Vectibix® dose reductions and delays, along with the reasons for reductions and delays will be summarized.

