#### **End of Observation Visit**

Documentation at the end of observation visit is required (defined as completion of 12-month observation period, death, withdrawal of consent, or loss to follow-up; whichever occurs first):

- Date and reason for ending study:
  - 12-month observation period reached
  - Discontinuation of Vectibix® treatment – date and reason for ending Vectibix® treatment
  - Death – date and primary cause of death to be recorded
  - Loss to follow-up
  - Withdrawal of informed consent
- Planned anti-cancer treatments initiated post Vectibix® discontinuation
- SADRs and ADRs to Amgen product

---

**Statistical Considerations:** The analysis of this study will be descriptive in nature. The data will be summarised for mCRC subjects with wild-type *KRAS* status who received Vectibix® as first-line treatment in combination with FOLFOX and separately for subjects who received Vectibix® in combination with FOLFIRI as second-line treatment in subjects who have received first-line fluoropyrimidine-based chemotherapy (excluding irinotecan). The data will be summarized by country. Selected sensitivity analyses may be performed if appropriate. For continuous outcomes, the mean, standard deviation, median, and range will be provided. For categorical variables, the frequency and percentage will be displayed. The percentage with two-sided 95% CI for the treatment pattern of Vectibix® (eg, cumulative proportion (over specified time period) of subjects with Vectibix® dose change) will be calculated. Duration of exposure, total number of infusions received, and the chemotherapy combined with Vectibix® will be summarized.

**Rationale:** The data being collected is to anticipate expected reimbursement agency requirements in Germany and France. The requirements focus on gaining a clear understanding of the real life use of Vectibix® in accordance with the new label, and so the objectives in this study have been defined to meet such requirements. This study will thus be conducted to gain understanding of Vectibix® use for the treatment of subjects with wild-type *KRAS* mCRC, in first-line in combination with FOLFOX or second-line in combination with FOLFIRI in routine clinical practice.

Figure 1. Sample Selection Flowchart

[figure not shown]
[figure not shown]

Figure 2. Study Design and Follow-up Schema

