### **3.3 Estimated Study Duration**

#### **3.3.1 Study Duration for Participants**

The duration of observation will vary for each subject. Subjects will be followed-up until approximately 30 days after the end of Vectibix® treatment, death, withdrawal of consent, loss to follow-up, or up to 12 months from the first dose of Vectibix®, whichever occurs first.

---

It is anticipated that subject enrolment will be ongoing for 12 months.

Including the 12-months observation period for each subject, it is anticipated the study duration will be approximately 24 months.

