### **5. STATISTICAL CONSIDERATIONS**

#### **5.1 Study Size**

This study will enrol approximately 740 subjects (up to 350 in France and up to 390 in Germany) in total. Enrolment into the study will be capped by country according to these numbers. Statistical properties of the study size are described in [Section 5.3](#). These samples sizes are consistent with previous submissions to reimbursement agencies.

---

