### 5.3 Sample Size Considerations

The analysis of this study will be descriptive in nature. Consequently, the sample size has not been assessed in terms of statistical power but with regards to what precision might be expected when examining categorical data such as type of anticancer therapy and discontinuation of Vectibix®. Proportions and confidence intervals will be most useful if reported in subgroups rather than overall. For instance the majority (perhaps 60%) of subjects recruited will be receiving first line treatment; their treatment patterns are expected to be different from second line subjects. Similarly, first line subjects with potentially resectable tumours (around 20%) will have different treatment patterns to those with unresectable tumours. Thus, we will have three important subgroups (the number of resectable subjects in the second line is expected to be negligible), consisting of 12% (line 1 potentially resectable), 48% (line 1 unresectable) and 40% (line 2) of the subjects in each country.

Table 1 below lists the expected precision of binomial estimates (in terms of half-width of a 95% confidence interval) using the planned sample sizes in the above scenarios. The expected precision in most of the subsets will be smaller than 10% but could be as high around 15% in Line 1 potentially resectable subjects.

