### **Vectibix® Discontinuation**

The number and percentage of subjects who discontinue Vectibix® during the observational period, along with the reasons for discontinuation will be summarized.

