#### **5.6.2.2 Secondary Outcomes**

##### **(i) Healthcare Resource Utilization**

Hospitalizations will be summarized including the type of hospitalization (outpatient, inpatient, ER, ICU, standard of care), the duration of hospitalization (days) as well as the reason for the hospitalization. Disease monitoring will also be summarized by type of visit (eg, GP or Specialist). Specialist visits as well as tumour assessment and methods (type of scans) occurrence and frequency will be summarized using descriptive statistics.

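### Sections 5.6.2.1 and 5.6.2.2 fix crude summaries with no handling of subjects lost or withdrawn on treatment, and no time basis for resource use

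*Protocol*

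**What the plan says.** Section 3.3.1: "The duration of observation will vary for each subject". Observation runs to about 30 days after Vectibix ends, or to death, withdrawal, loss to follow-up or 12 months from first dose, whichever comes first. Enrolment takes 12 months of a study lasting about 24, so every subject can reach the cap.

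Section 5.6.2.1, exposure: "duration of exposure will be calculated as the number of months between the date of the first and last Vectibix® infusions", counted within the observation period. Cumulative dose and number of infusions cover the same window. Section 5.6.1 gives mean, SD, median and range for continuous outcomes.

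Section 5.6.2.1, discontinuation: "The number and percentage of subjects who discontinue Vectibix® during the observational period", with reasons. Dose reductions and delays are also counts and percentages. The synopsis (Statistical Considerations) instead gives as an example a "cumulative proportion (over specified time period) of subjects with Vectibix® dose change", with a 95% CI.

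Section 5.6.2.2, resource use: "Specialist visits as well as tumour assessment and methods (type of scans) occurrence and frequency will be summarized using descriptive statistics". Hospitalisations are summarised by type, duration and reason. No person-time denominator is named.

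Section 4.1 keeps the data of subjects who withdraw up to the date of withdrawal. The End of Observation list in Section 4 records loss, withdrawal, death and the 12-month mark separately from discontinuation.

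**The concern.** A subject who withdraws or is lost while still receiving Vectibix has an unknown treatment end. Under the fixed definitions this subject stays in the denominator, contributes a duration that stops at the last recorded infusion, and is not counted as a discontinuer. Both effects push the estimates down: shorter duration, lower discontinuation. The logistic and general linear models of Section 5.6.1 take the same values as outcomes. Section 5.6.2.1 also does not say whether death on treatment counts as discontinuation, so the numerator of that percentage is open.

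Resource use raises a different issue. Observation normally ends about a month after treatment stops, so subjects treated longer are watched longer and accumulate more visits and admissions at the same rate.

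Exposure and discontinuation are primary outcomes, and the stated purpose is to inform reimbursement agencies. They may read a mean duration as total treatment time, or read counts per subject as a difference in resource intensity between lines.

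**Working it through.** **The plan's own figure.** Sample size was set by precision, "in terms of half-width of a 95% confidence interval". With half-width = 1.96 × √(p(1−p)/n), p = 0.5 gives 1.96 × √(0.25/350) = 5.24% for France and 1.96 × √(0.25/390) = 4.96% for Germany. Table 1 prints 5.2% and 5.0%. All 24 entries reproduce with the n printed in the table.

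**Inputs for the illustration.**
- From the protocol: 12-month cap, about 30 days (taken as 1 month) of observation after treatment, and PFS medians of 10.0 months (FOLFOX) and 6.7 months (FOLFIRI) in Section 2.2.2.
- Assumed: time on treatment is exponential, with those PFS medians as a proxy. Loss or withdrawal on treatment is independent and exponential, with 12-month probability d = 5, 10 or 20%. The protocol gives no rate.

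**Step 1: the cap alone.** With λ = ln 2 / median, the proportion still treated at 12 months is S = 2^(−12/median) and the mean within 12 months is (1−S)/λ.
- Median 6.7: S = 0.289, discontinued 71.1%, mean 6.87 months (uncapped 1/λ = 9.67).
- Median 10.0: S = 0.435, discontinued 56.5%, mean 8.15 months (uncapped 14.43).

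With nobody lost, the crude percentage equals the true 12-month percentage, and the observed median is unchanged at 6.7 or 10.0. Only the mean changes meaning.

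**Step 2: add loss on treatment.** With g = −ln(1−d)/12 and E = 1 − exp(−12(λ+g)):
- crude discontinuation = λ/(λ+g) × E
- observed mean = E/(λ+g)
- observed median = ln 2/(λ+g)

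For median 6.7 and d = 10%: λ = 0.1035, g = 0.0088, E = 0.740, so crude discontinuation = 0.922 × 0.740 = 68.2%.

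| Median | d | Share lost on treatment | Crude discontinuation | Shift (points) | Observed median | Observed mean |
|---|---|---|---|---|---|---|
| 6.7 | 5% | 2.9% | 69.7% | −1.4 | 6.43 | 6.73 |
| 6.7 | 10% | 5.8% | 68.2% | −2.9 | 6.18 | 6.59 |
| 6.7 | 20% | 11.7% | 65.2% | −5.9 | 5.68 | 6.30 |
| 10.0 | 5% | 3.4% | 55.2% | −1.2 | 9.42 | 7.97 |
| 10.0 | 10% | 6.8% | 54.0% | −2.5 | 8.88 | 7.79 |
| 10.0 | 20% | 13.8% | 51.4% | −5.1 | 7.88 | 7.41 |

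Shifts are taken before rounding. The share lost is below d because many subjects stop treatment first.

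**Step 3: against the planned precision.** A true 70% corresponds to the p = 0.3 row of Table 1. The half-widths there are 4.8 points (France, all) and 4.5 (Germany, all). By line in France they are 7.6 (second line, n = 140) and, for first line with n = 42 + 168 = 210, 1.96 × √(0.21/210) = 6.2. The shift exceeds a whole-country half-width only near 20% loss and stays below these by-line values. Unlike the half-width, it does not shrink with more subjects.

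**Step 4: resource use.** Observed time is min(T+1, 12), with mean 1 + (1 − exp(−11λ))/λ.
- Median 6.7: 1 + 0.680/0.1035 = 7.57 months.
- Median 10.0: 1 + 0.533/0.0693 = 8.70 months.

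The ratio is 8.70/7.57 = 1.15. At 0.1 admissions per month in both lines, that is 0.87 against 0.76 admissions per subject.

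**The case against.** The strongest reply is that the protocol limits every exposure measure to the observation period, the cap is the same for everyone, and most variation in follow-up arises because treatment stopped, which is the event of interest and is then fully observed. Dose changes can occur only on treatment, so their crude percentage is a valid on-treatment proportion except for subjects lost while treated. The study is descriptive, "the sample size has not been assessed in terms of statistical power", follow-up duration will be reported, and estimator details may sit in a SAP that is not at hand. All of this stands, and it limits the point.

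Two stronger readings are therefore not supported. A reader might infer that the cap makes the primary estimates biased, with the mean about 29-44% too low (6.87 against 9.67 months; 8.15 against 14.43). The protocol does not claim an uncapped mean, and a 12-month restricted mean gives the same 6.87 and 8.15 when nobody is lost. A reader might also divide 8.15 by 6.87 and report 19% more visits in first line. That omits the month of observation after treatment, and resource use is a secondary outcome.

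The synopsis wording on dose change is an example, so it is a looser text to align rather than a clear contradiction.

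The reply does not cover subjects lost or withdrawn on treatment. The protocol itself fixes the definitions and percentages, and a SAP that follows them inherits the gap.

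**Conclusion.** The point holds in limited form and should be fixed. The fixed summaries mishandle subjects lost or withdrawn on treatment, and resource use has no time basis. Under the assumptions above, 12-month discontinuation is understated by about 1-6 points. Median duration falls from 10.0 to 9.4-7.9 months, or from 6.7 to 6.4-5.7. First-line resource use per subject appears about 15% higher at equal rates.

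The true size is unknown, because the loss rate is not given and PFS is only a proxy for time on treatment. With no loss, the discontinuation percentage and the median are correct as planned, and only labelling and the resource-use denominator remain. If loss is related to prognosis, censoring methods reduce the problem but do not remove it. Section 4.3.1 warns of limited data on deceased patients in Germany, so the cause of loss deserves a look by country.

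**What to change.** In Section 5.6.2.1:
- Estimate time from first infusion to permanent Vectibix discontinuation by Kaplan-Meier, or by cumulative incidence, censoring at loss, withdrawal or 12 months on treatment. State whether death on treatment is an event or a competing event.
- Report the median and the 12-month proportion with 95% CI, by line and country.
- Report dose reductions and delays as a cumulative proportion over a stated period, in line with the synopsis.
- Label mean duration, cumulative dose and number of infusions as within 12 months.

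In Section 5.6.2.2, report visits, hospitalisations and hospital days per patient-month alongside the counts.

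The cost is wording and slightly more analysis work. Start and stop dates and the date and reason for ending observation are already collected, so neither the design nor the case report form changes.

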### **Vectibix® Discontinuation**

The number and percentage of subjects who discontinue Vectibix® during the observational period, along with the reasons for discontinuation will be summarized.

#### **5.6.2.2 Secondary Outcomes**

##### **(i) Healthcare Resource Utilization**

Hospitalizations will be summarized including the type of hospitalization (outpatient, inpatient, ER, ICU, standard of care), the duration of hospitalization (days) as well as the reason for the hospitalization. Disease monitoring will also be summarized by type of visit (eg, GP or Specialist). Specialist visits as well as tumour assessment and methods (type of scans) occurrence and frequency will be summarized using descriptive statistics.

### **Baseline Characteristics Description of the Subject**

Descriptive statistics will be used to summarize subject demographic and baseline characteristics including age, sex, height, body weight, performance status, co-morbidities and prior treatment history. The duration of follow-up will also be summarized.

### **Response Rate**

Response to Vectibix®, if documented, including best response, conversion to resectability will be summarized using the local tumour response analysis set.

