#### Follow-up Observation Period

Data obtained after the initiation of Vectibix® in combination with chemotherapy, and subsequently during the remainder of the 12-month observational period will similarly be abstracted onto the eCRF (or paper CRF) based on physician preferences for follow up.

Follow-up data post initiation of Vectibix® treatment will be collected at the next patient visit (based on physician preferences for follow up) throughout the observation period until 30 days after the end of Vectibix® treatment, death, withdrawal of consent, loss to follow-up, or up to 12 months from the first dose of Vectibix®, whichever occurs first.

This data will include the following (where available and recorded as standard clinical practice):

- Vectibix® treatment pattern including:
  - start and stop dates
  - dose and schedule
  - total number of infusions received
  - dose reductions, dose delays, and reasons for dose reductions or delays
  - reason for treatment discontinuation
- Concomitant anticancer therapy for mCRC including surgical procedures, radiotherapy, chemotherapy, biological therapy and/or other systemic anticancer therapy and other procedures. Data to include:
  - type of therapy
  - start and stop dates
  - dose, route, and frequency (if applicable)
  - reason for cessation of therapy
- Tumour response follow up (radiological imaging of sites of disease, investigator's assessment of tumour response)
- Resection status
- Healthcare resource utilization including type of visit (inpatient, outpatient, ER, other) and reason for hospitalisations
- Relevant concomitant medication
- SADRs and ADRs to Amgen product

---

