### **4.3 Internal Validity of Study Design**

#### **4.3.1 Selection Bias**

We do anticipate some degree of selection bias within our study. Since we are not recruiting patients until they have been dosed with Vectibix® at least once, there is a

small group of patients who we will not be sampling ie, those who do not commence treatment, or cease treatment very soon after the first dose, usually because of death or disease progression. Therefore the response rate may be inflated slightly and other collected data impacted. Note that in Germany we may only be able to obtain limited data from deceased patients. However generally for most patients this will not limit inclusion of patient data into the study as the study is mainly prospective in design and patients will be alive at study enrolment (where consent is required). Should subjects die during the course of the study it may become more difficult to obtain complete follow up information if the notes are then subsequently filed elsewhere and we need informed consent to obtain them.

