#### Secondary:

- The following will be described and tabulated
  - Healthcare resource utilization, including type of visit (inpatient, outpatient, ER, other) and reason for hospitalisation
  - Demographics, disease characteristics, co-morbidities, individual treatment goals and prior treatment history
  - Response to Vectibix®, if documented, including best response, conversion to resectability, and by individual treatment goals
  - Summaries of planned anti-cancer treatment post initiation post Vectibix® discontinuation

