### 5.2.2 Analysis Subsets

First Line FOLFOX Analysis Set (FLFAS): all enrolled subjects who have received at least one infusion of Vectibix® in combination with FOLFOX as first-line treatment, a maximum of 42 days before entering study.

Second Line FOLFIRI Analysis Set (SLFAS): all enrolled subjects who have received at least one infusion of Vectibix® in combination with FOLFIRI as second-line treatment and have received first-line fluoropyrimidine-based chemotherapy (excluding irinotecan), a maximum of 42 days before entering study.

FLFAS and SLFAS are the primary analysis sets for all analyses. Selected sensitivity analyses may be performed to assess the impact of using other analysis sets.

The data will be summarized by country to fulfil local post reimbursement requirements.

---

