#### 5.6 Planned Methods of Analysis

##### 5.6.1 General Approach/Considerations

The analysis of this study will be descriptive in nature. The data will be summarized for subjects with metastatic colorectal cancer (mCRC) with tumour expressing wild-type (non-mutated) *KRAS* who received Vectibix® in combination with FOLFOX as first-line

---

treatment and subjects who received Vectibix® in combination with FOLFIRI as second-line treatment and received first-line fluoropyrimidine-based chemotherapy (excluding irinotecan). The data will be summarized by country to fulfil local post reimbursement requirements. For continuous outcomes, the mean, standard deviation, median, and range will be provided. For categorical variables, the frequency and percentage, with two-sided 95% CI, will be displayed for the treatment pattern of Vectibix®. Summary tables and analyses will be based on FLFAS and SLFAS and corresponding local tumour response analysis sets.

For each outcome parameter, the covariates listed in [Section 5.2.3](#) will be assessed in a logistic or general linear model. Non-significant factors will be eliminated stepwise until only covariates significant at the 5% level remain, thereby indicating which covariates have an important influence on treatment pattern. Summary statistics will then be reported for each level of the significant covariates.

Selected sensitivity analyses may be performed to assess the impact of protocol deviations using other analysis sets.

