## **6. STUDY LIMITATIONS**

(See also [Section 4.3](#) and [Section 4.4](#))

There are two potential limitations regarding subject selection:

- (i) Centre level refusals
- (ii) Patient level refusals, again

We shall review carefully refusals at the centre and patient level and, if appreciable, qualify the results accordingly.

---

Another potential limitation is that medical practice may be affected by participation in the study (Hawthorne effect). This could affect the initial treatment decision for subjects who start treatment after a centre has been initiated. The main limitations in this study relate to the ability to include a sufficient sample of patients that meet the eligibility criteria and that are being treated with Vectibix® according to the label specified. We shall be including a large number of centres to allow us to capture an adequate study population that represents patients being prescribed Vectibix® in France and Germany according to the label. The results should therefore be generalizable to patients on Vectibix® in these two countries and in addition to countries nearby that have similar health care systems. As the study design is mainly prospective, this will minimize missing data. There is a risk that there will be some incomplete data and that it will not be possible to go back to the medical records to complete it adequately so that incomplete data may need to be excluded from the analysis. We will be performing frequent data extractions to review any inconsistencies within the data.

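### Response is to be summarised in an undefined response set that conflicts with the analysis sets of Section 5.2.2; if entry requires a documented response, the rate would probably be biased upward

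*Protocol*

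**What the plan says.** Section 5.2.2 defines only the first-line FOLFOX set (FLFAS) and the second-line FOLFIRI set (SLFAS). Membership rests on enrolment and treatment; for first line it is "all enrolled subjects who have received at least one infusion of Vectibix® in combination with FOLFOX as first-line treatment", within the stated window before entry. The section then says: "FLFAS and SLFAS are the primary analysis sets for all analyses". Other sets are mentioned there only for optional sensitivity analyses.

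Section 5.6.1 adds a further kind of set: "Summary tables and analyses will be based on FLFAS and SLFAS and corresponding local tumour response analysis sets". Section 5.6.2.2 assigns response to it: "Response to Vectibix®, if documented, including best response, conversion to resectability will be summarized using the local tumour response analysis set". The outcome list in Section 5.2.1 carries the same condition: "Response to Vectibix®, if documented, including best response, conversion to resectability, and by individual treatment goals". Neither Section 5.2.2 nor the glossary lists the response set.

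On data sources, the follow-up part of Section 4 collects "Tumour response follow up (radiological imaging of sites of disease, investigator's assessment of tumour response"), where available and at the physician's preferred follow-up. Section 4.3.1 says of recruiting only after a first dose: "Therefore the response rate may be inflated slightly and other collected data impacted". Section 6 notes that some "incomplete data may need to be excluded from the analysis".

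**The concern.** Two things are at stake. The first is a plain inconsistency: one section makes FLFAS and SLFAS primary for everything, and two others move response to a set whose membership is not given.

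The second follows from one natural reading of that set. Every subject must have baseline imaging (Section 3.5.6), so a set defined by baseline imaging alone would contain nearly everyone and would hardly need its own name. A set requiring a documented post-baseline response is therefore a plausible reading, though this is inference. Under it, exclusion may well be linked to outcome:

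- No assessment schedule is imposed (Section 4).
- Observation ends about 30 days after the last treatment (Section 3), so early stoppers have little time to be assessed.
- Section 4.3.1 warns that data on deceased patients may be limited in Germany.

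Since results are summarised by country for reimbursement purposes, the share documented could differ between the two countries reported.

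Conversion to resectability is placed in the same set, with no restriction to subjects who were not resectable at the start.

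**Working it through.** The protocol gives no expected response rate, evaluable share or response-set size for this study, so it has no figure of its own to reproduce. The check asks how far a documented-only rate could sit from the all-subjects rate.

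**Inputs**

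- R, the response rate in all treated subjects: 57% (first line) and 36% (second line). These are the panitumumab-arm rates of the two pivotal studies in Section 2.2.2, used for illustration only.
- u, the share with no documented response: assumed, 5% to 30%.
- f, the response rate in those subjects as a fraction of R: assumed 0, 0.5 and 1.
- Subjects per line: 60% of 740 = 444 and 40% of 740 = 296 (shares from Section 5.3).

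**Formulas**

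Documented-only rate = R(1 − u·f)/(1 − u)

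Excess over R = R·u·(1 − f)/(1 − u)

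**At u = 10%**

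- First line, f = 0: 0.57 × 0.10/0.90 = 6.3 points (63.3% against 57%).
- First line, f = 0.5: 0.57 × 0.10 × 0.5/0.90 = 3.2 points (60.2%).
- Second line, f = 0: 0.36 × 0.10/0.90 = 4.0 points (40.0% against 36%).
- Second line, f = 0.5: 0.36 × 0.10 × 0.5/0.90 = 2.0 points (38.0%).
- Either line, f = 1: no excess.

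**Over the assumed range (documented-only rate, excess in points)**

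| u | First line, f = 0 | First line, f = 0.5 | Second line, f = 0 | Second line, f = 0.5 |
|---|---|---|---|---|
| 5% | 60.0% (+3.0) | 58.5% (+1.5) | 37.9% (+1.9) | 36.9% (+0.9) |
| 10% | 63.3% (+6.3) | 60.2% (+3.2) | 40.0% (+4.0) | 38.0% (+2.0) |
| 20% | 71.2% (+14.2) | 64.1% (+7.1) | 45.0% (+9.0) | 40.5% (+4.5) |
| 30% | 81.4% (+24.4) | 69.2% (+12.2) | 51.4% (+15.4) | 43.7% (+7.7) |

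If the undocumented responded better than average (f = 1.2), the documented-only rate at u = 10% would be too low, by 1.3 and 0.8 points.

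**Against sampling error.** The 95% half-width is 1.96·√(R(1 − R)/n). This gives 1.96·√(0.57 × 0.43/444) = 4.6 points in first line and 1.96·√(0.36 × 0.64/296) = 5.5 points in second line, countries pooled. At u = 10% only the first-line excess with f = 0 is larger than its half-width.

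**What counting the undocumented as non-responders does.** That rate is R(1 − u·f). In first line at u = 10% it is 57% if f = 0, 0.57 × 0.95 = 54.2% if f = 0.5, and 0.57 × 0.90 = 51.3% if f = 1. So it equals R when none of the undocumented responded and is too low otherwise. The documented-only rate equals R when f = 1. For any f between 0 and 1 the two rates enclose R.

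**The case against.** The strongest objection is that nothing in the protocol says who belongs to the response set. In Section 5.6.2.2 the condition about documentation attaches to the response, not to entry into the set, and Section 5.6.1 says only that the sets correspond to FLFAS and SLFAS. A set defined by baseline disease fits the text too and would keep early failures. A reader might infer that the plan removes early failures and therefore inflates the response rate. The documents do not support that as a stated consequence; it is a risk under one reading.

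Other points also stand in part:

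- Set membership and the handling of missing assessments are often settled in a statistical analysis plan, which was not available here. The missing definition alone is therefore not the finding; the conflict between Sections 5.2.2, 5.6.1 and 5.6.2.2 is.
- An investigator's assessment counts as response data, so progression without a scan can be documented.
- The Section 6 remark on incomplete data is a general limitation, not a rule for response.
- Counting undocumented subjects as non-responders does not remove the dependence on how often centres assess. It reverses the direction. This is why both rates are needed.
- Section 5.6.2.2 already plans to summarise the frequency of tumour assessments, so assessment intensity will be visible, though not tied to the response denominator.
- Section 5.2.1 reports response by treatment goal, and Section 5.3 distinguishes potentially resectable from unresectable first-line subjects. Neither fixes a denominator for conversion.

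**Conclusion.** The inconsistency is established: response sits in a set that the analysis-set section neither lists nor allows as primary. Upward bias is conditional. It needs a set that requires a documented post-baseline response, and undocumented subjects who respond less often than the rest. The lack of a fixed schedule and the limited data expected after death make this plausible, and it would be a separate source from the enrolment effect conceded in Section 4.3.1.

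The size cannot be stated for this study. At an assumed 10% undocumented it runs from zero to 6.3 points in first line and from zero to 4.0 points in second line, as the undocumented go from responding equally to not at all. Rates near 71% and 45% come only from assuming 20% undocumented with no responders among them, and should not be read as predictions.

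The primary objective is pattern of use. Response is a secondary, descriptive outcome with no hypothesis test, so severity is minor to moderate.

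**What to change.** 1. Reconcile Section 5.2.2 with Sections 5.6.1 and 5.6.2.2. Either define the response set in 5.2.2 and state its role, or remove it.
2. Report best response on all FLFAS and all SLFAS subjects, with a displayed category for not assessed or not documented that stays in the denominator.
3. Beside it, give the documented-only rate and the percentage documented, by country, so that the two rates bracket the effect of differing assessment intensity.
4. Report conversion to resectability among subjects not resectable at baseline. Resection status is already a baseline item; confirm that it records resectability.

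The cost is protocol and analysis-plan wording plus a few table rows, with no new data provided the baseline item serves. The downside is that the all-subjects rate is lower and is conservative where documentation is sparse.
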